10. CLINICAL MONITORING

10.1. Site Monitoring Plan

Site monitoring is conducted to ensure that the human subjects' protections, study and laboratory procedures, study intervention administration, and data collection processes are of high quality and meet sponsor, ICH/GCP guidelines and applicable regulations, and that this trial is conducted in accordance with the protocol, protocol-specific MOP and applicable sponsor standard operating procedures. The sponsoring agency, or its designee will conduct site-monitoring visits as detailed in the clinical monitoring plan.

Site visits will be made at standard intervals as defined by the study team and may be made more frequently as directed by the PIs. Monitoring visits will include, but are not limited to, review of regulatory files, accountability records, eCRFs, informed consent forms, medical and laboratory reports, and protocol and GCP compliance. Site monitors will have access to each participating site, study personnel, and all study documentation according to the approved site monitoring plan. Study monitors will meet with site principal investigators to discuss any problems and actions to be taken, and will document site visit findings and discussions.

11. STATISTICAL CONSIDERATIONS

11.1. Study Hypotheses

Primary outcome

The null hypothesis that there is no difference in cure rate assessed by microscopy at 4 weeks between children who received 40 mg/kg praziquantel and children who received 80 mg/kg praziquantel. This will be tested against the alternative hypothesis that there is a difference in cure rate at 4 weeks between children who received 40 mg/kg praziquantel and children who received 80 mg/kg praziquantel, and will be a superiority comparison.

Secondary outcomes

All secondary outcomes will be superiority comparisons, with alternative hypothesis of a difference in the outcome between the two sets of participants being compared.

For outcomes 1 to 5 below, the null hypothesis is that there is no difference in the outcome between children in the 40 mg/kg praziquantel group and children in the 80 mg/kg praziquantel group.

1. Mean egg reduction rate at 4 weeks
2. Schistosomal antigenic clearance assessed by CCA at 4 weeks
3. Schistosomal antigenic clearance assessed by CAA at 4 weeks
4. Prevalence of any adverse event within 3 hours of dosing

Adverse events will be classified by type. Adverse event types that occur with overall prevalence >5% or at prevalence >5% in either setting will also be tested for differences between trial arms.

5. (a) Prevalence of adverse event type 1 within 3 hours of dosing
(b) Prevalence of adverse event type 2 within 3 hours of dosing
(c) Prevalence of adverse event type 3 within 3 hours of dosing
continued for all adverse event types occurring with prevalence >5%

For secondary outcomes 6 to 13 below, two null hypotheses will be tested. The first null hypothesis is that there is no difference in the morbidity outcomes between children who received six-monthly praziquantel (either 40 mg/kg or 80 mg/kg) and children who received 12-monthly praziquantel (either 40 mg/kg or 80 mg/kg). The second null hypothesis is that there is no difference in the morbidity outcomes between children who received 40 mg/kg praziquantel (regardless of dosing schedule) and children who received 80 mg/kg praziquantel (regardless of dosing schedule).

6. Mean weight-for-height z-score at 12 months
7. Proportion with weight-for-height z-score at 12 months < -2
8. Mean MUAC-for-age z-score at 12 months
9. Proportion with MUAC-for-age z-score at 12 months < -2
10. Mean height-for-age z-score at 12 months
11. Proportion with height-for-age z-score at 12 months < -2
12. Mean haemoglobin level at 12 months
13. Proportion with anaemia at 12 months
14. Exploratory: EED markers
15. Exploratory: immune responses to *S. mansoni* infection and treatment
16. Exploratory: prevalence and pattern of schistosomiasis-related morbidity by ultrasound scan.

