3.1.2. Secondary

To assess the **safety and** efficacy and PK/PD of PZQ administered at different dose regimens.

- 3.1.2.1. To evaluate the PK/PD of both PZQ enantiomers given the concern that this has varied in studies of *S. mansoni*.
- 3.1.2.2. To expand PD endpoints for drug efficacy to include state-of-the art antigen tests to accurately capture residual worm burden (Circulating Cathodic and Anodic Antigens (CCA and CAA)).
- 3.1.2.3. To assess the safety and impact of PZQ treatment (dose and interval) on key measures of morbidity 6 and 12 months after initial treatment and mechanisms mediating morbidity
- 3.1.2.4. To further evaluate the safety of higher PZQ dosing (80 mg/kg) including bone marrow, renal, and liver toxicity as captured before dosing and 12 hours after.
- 3.1.2.5. To evaluate the impact of different doses (40 vs. 80 mg/kg) and varying dosing intervals (every 6 or 12 months) on iron status, hemoglobin, and age and gender adjusted longitudinal growth and nutritional status as captured by height and weight for age, and weight for height z-scores as determined by WHO Anthro.
- 3.1.2.6. To evaluate the mechanistic role of *Environmental Enteric Dysfunction (EED)* in the pathogenesis of schistosomiasis related morbidities. We will capture state of the art biomarkers of EE including fecal calprotectin, urine lactulose:mannitol ratio, serum

endotoxin, serum endotoxin core antibody, and pro- inflammatory cytokines and employ Path Modeling techniques to identify mechanistic pathways.

- 3.1.2.7. To assess the role of Environmental Enteric Dysfunction (EED) in inter-individual variability in PZQ area under the curve (AUC) PK parameters demonstrated in this age group.
- 3.1.2.8. To explore immune responses to *S. mansoni* infection and treatment
- 3.1.2.9. To assess the prevalence and the pattern of schistosomiasis-related morbidity as determined by ultrasound scan.

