11.2. Sample Size Considerations

The sample size calculations are based on the primary outcome of cure rate at 4 weeks. Cure rate is defined as the proportion of individuals who are uninfected at the follow-up, where infection will be assessed using parasitological methods. The null hypothesis is that cure rate at 4 weeks is the same between children who received 40 mg/kg praziquantel and children who received 80 mg/kg praziquantel. The null hypothesis will be tested using a chi-squared test statistic. The analysis population will be comprised of all participants as randomised, regardless of whether or not they received the allocated treatment (intention-to-treat).

Data from Uganda found cure rates for *S. mansoni* infected 3-9 year olds of 70% and 82% for 40 mg/kg and 60 mg/kg praziquantel, respectively. We anticipate that cure rates may be lower in younger children and that the 80 mg/kg dose will have a higher cure rate than the 60 mg/kg. However, we conservatively power the trial to detect a difference in cure rate of 70% versus 82%. Using a two-sided 5% significance level, approximately 173 children per trial arm will be required for 80% power and 232 per arm (N=464) for 90% power to detect a difference in cure rate at 4 weeks between the trial arms. Allowing for loss to follow-up of 7%, a total of approximately 500 children will be required. A sample size of 600 will allow us adequate power to examine sub-groups such as younger (12-30 months) versus older (30-47 months) children, particularly given that the effect size is likely to be larger based on a higher dose (80 mg/kg).

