11.4. Analysis Plan

A trial flow chart will be constructed, showing the number of children screened, enrolled and randomised, together with reasons for exclusion at each stage. Baseline characteristics of trial participants will be summarised by trial arm. Numbers and proportions will be reported for categorical characteristics. Means, standard deviations, medians and ranges will be used for continuous characteristics.

All trial analyses will be done using the intention-to-treat population, i.e. all children will be included as randomised, regardless of whether or not they received the allocated treatment. Children will contribute to 4 week outcomes if they are assessed within 1 week of the 4 week time point. Children will contribute to 6 and 12 month outcomes if they are assessed within 2 weeks of these time points. Since loss to follow-up is expected to be low at 4 weeks, only children for whom outcome data are available will be included in analyses (complete case analysis), with no imputation of missing outcome data planned.

The primary outcome of cure rate will be compared between trial arms using a chi-squared test statistic. The difference in proportions cured and a corresponding 95% confidence interval will be calculated. The related primary outcome, egg reduction rate, is defined as the percentage decrease in egg count between baseline and follow-up. The mean egg reduction rate will be compared between trial arms using a t-test, with the difference in mean egg reduction rate and its 95% confidence interval calculated. Schistosomal (CCA and CAA) antigenic egg clearance outcomes will be analyzed using the same approach as for cure rate (based on microscopy).

Prevalence of adverse events (both any and separately for types of event that occur with overall prevalence >5%) will be compared between trial arms using chi-squared tests. Rare adverse events will be tabulated by trial arm but no formal statistical comparisons done. Severity of adverse events will also be tabulated, by trial arm.

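### Adverse events are compared between doses by chi-squared test alone; without a risk difference and confidence interval, a non-significant result does not show what excess at 80 mg/kg has been excluded

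*Combined protocol and SAP*

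**What the plan says.** Safety of the higher dose is a named secondary objective in section 3.1.2 (item 3.1.2.4): "To further evaluate the safety of higher PZQ dosing (80 mg/kg". Section 2.3.1 describes exposure to a higher dose than usual as the main risk of the trial.

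Section 11.1 sets the hypotheses: "All secondary outcomes will be superiority comparisons, with alternative hypothesis of a difference in the outcome between the two sets of participants being compared". Outcome 4 is "Prevalence of any adverse event within 3 hours of dosing". Outcome 5 repeats this for each event type whose prevalence exceeds 5% overall or in either setting. For both, the null is no difference between 40 and 80 mg/kg.

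Section 11.4 gives the methods. For cure rate: "The difference in proportions cured and a corresponding 95% confidence interval will be calculated". For egg reduction rate it likewise asks for the difference in means and its 95% interval. Adverse-event prevalence, by contrast, "will be compared between trial arms using chi-squared tests", with no estimate or interval named. The rest is descriptive: "Rare adverse events will be tabulated by trial arm but no formal statistical comparisons done" and "Severity of adverse events will also be tabulated, by trial arm".

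Section 11.2 justifies the sample size on cure rate, growth, haemoglobin, pharmacokinetics and immunology. It gives no power or precision for adverse events.

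**The concern.** The safety question is how large an excess of adverse events at 80 mg/kg the data can rule out. A test against a null of no difference can detect harm, but when it fails to reject it says nothing about the size of harm still possible. With only a p-value specified, a report could show a non-significant result and leave the reader unable to tell a precise finding of little excess from an imprecise one.

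The stake is what the trial can say under objective 3.1.2.4. The same data would support a quantified statement if the estimate and interval already planned for efficacy were also planned for harm.

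**Working it through.** **The plan's own figure.** There is none for adverse events. The only two-proportion sizing is for cure, 70% v 82%: "Using a two-sided 5% significance level, approximately 173 children per trial arm will be required for 80% power", and 232 per arm for 90% power. The standard two-sided formula is

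n = [1.96·√(2p̄(1−p̄)) + 0.8416·√(p₁(1−p₁)+p₂(1−p₂))]² / d²

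With p̄ = 0.76 and d = 0.12, n = (1.1838 + 0.5033)² / 0.0144 ≈ 198 per group. For 90% power it is 265. The stated figures are not reproduced. A one-sided 5% calculation with continuity correction gives 172 and 232. This is a separate matter: at 300 per dose the cure comparison has about 93% two-sided power.

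**Inputs for adverse events.**
- 300 children per baseline dose: two arms of 150 at each dose (Table 1).
- Two-sided 5% level: stated in 11.2 and consistent with the non-directional alternative in 11.1.
- Background rates of 5% to 50%: assumptions. The documents give no rate for this age and dose.
- No losses.

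**Chance of missing a true excess.** Let x and y be the numbers of children with an event at 40 and 80 mg/kg, and p̄ their pooled proportion. The uncorrected statistic is

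χ² = [(y−x)/300]² / [2p̄(1−p̄)/300]

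The miss probability is the sum of the binomial probabilities of all (x, y) with χ² ≤ 3.84. Exact enumeration gives:

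| True excess | 5% background | 10% | 20% | 30% | 50% |
|---|---|---|---|---|---|
| 3 points | 68% | 79% | 85% | 88% | 88% |
| 5 points | 34% | 54% | 69% | 74% | 76% |
| 8 points | 6% | 19% | 37% | 45% | 48% |
| 10 points | 1% | 6% | 19% | 27% | 30% |

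Hand check for 5% v 10%: (0.05·√300 − 1.96·√(2·0.075·0.925)) / √(0.0475+0.09) = (0.8660 − 0.7301)/0.3708 = 0.367. Power is Φ(0.367) = 0.64, so about 36% are missed, against 34% exactly.

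**What an interval adds.** Suppose 27/300 (9%) at 80 mg/kg and 15/300 (5%) at 40 mg/kg have an event. Then χ² = 3.69 and p = 0.055. The Wilson limits are 0.0626 to 0.1278 and 0.0305 to 0.0808. Newcombe's interval for the difference is:
- lower: 0.040 − √[(0.090−0.0626)² + (0.0808−0.050)²] = −0.001
- upper: 0.040 + √[(0.1278−0.090)² + (0.050−0.0305)²] = +0.082

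The result is non-significant but compatible with an 8.2-point excess. Likewise 45/300 v 30/300 gives p = 0.064 and an interval of −0.3 to +10.3 points.

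**Precision available.** If the true rates are equal, the half-width 1.96·√(2p(1−p)/300) is 3.5, 4.8, 6.4, 7.3 and 8.0 points at rates of 5, 10, 20, 30 and 50%. With no events in 300, the exact upper limit (two-sided 95%) is 1 − 0.025^(1/300) = 1.2%.

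**The window.** Outcome 4 counts events within 3 hours of dosing. Table 1 places the second dose 3 hours after the first. Section 3.2.2 (item 3.2.2.2) and section 9.1 use 12 hours. If the 3 hours run from the first dose, both groups have had only 40 mg/kg when the window closes. Neither the test nor an interval would then describe 80 mg/kg.

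**The case against.** A reader might infer that a non-significant test is the trial's only route to a safety conclusion. The documents do not support that. Severity and rare events are tabulated by arm (11.4). Section 9.5 sets halting rules. Section 9.6.2 allows the DSMB data by arm and unblinded, with a final review of cumulative safety data. No section says that p > 0.05 will be read as safe, and objective 3.1.2.4 is to evaluate safety, not to show non-inferiority. All this stands. It does not fill the gap: the halting rules count events per 100 enrolled without comparing doses, and neither the tabulations nor the DSMB text specifies an estimate of excess risk with its uncertainty.

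A reader might also infer that excesses anywhere from 3 to 10 points would often be missed. The upper end fails: a 10-point excess is missed only 1% to 19% of the time at background rates of 5% to 20%. Nor should very low rates such as 1% v 3% or 2% v 5% be used for event types. Their overall prevalences, 2% and 3.5%, fall mostly below the 5% threshold for testing, so such events would usually only be tabulated.

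A third inference is that the plan needs a binding maximum acceptable excess. That is debatable. It would turn a Phase II secondary outcome into a non-inferiority-type claim. At 300 per dose and equal true rates, power to exclude 5 points is 80% at a 5% background rate, but 53% at 10%, 33% at 20% and 23% at 50%.

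Finally, section 11.4 defers full details to a formal statistical analysis plan before database lock. That makes the change easy, but the deferral does not commit to intervals for adverse events, while the test is already named.

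**Conclusion.** The point holds as one of estimation. The only formal between-dose analysis of adverse events is a two-sided superiority chi-squared test without an effect estimate or interval, in a section that specifies both for efficacy. At 300 per dose a true 5-point excess would be missed about one time in three at a 5% background rate, about half the time at 10%, and about two times in three at 20%. Larger excesses are better covered: 10 points is detected with about 80% power or more while the background rate is about 20% or less.

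These figures assume the event rates shown, no losses, and a window that captures events after the second dose. That last condition is not secure as written. It would not be right to conclude that the trial has no other safety assessment, or that it intends to treat non-significance as proof of safety.

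**What to change.** In section 11.4, and in the formal statistical analysis plan:

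1. Report the risk difference, 80 minus 40 mg/kg, with a 95% interval (Newcombe or Miettinen-Nurminen) for any adverse event, each event type, Grade 3 events and serious adverse events. Where a group has no events, give the exact upper bound.
2. State that conclusions about the safety of the higher dose rest on the interval, and that a non-significant chi-squared test is not evidence of similar safety. Keep the chi-squared p-value as descriptive.
3. Reconcile the 3-hour window in 11.1 with the second dose at 3 hours and with the 12-hour window in sections 3.2.2 and 9.1, and say from which dose the window is counted. The interval is informative about 80 mg/kg only if the window covers the second dose.

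A pre-specified acceptable excess is optional and is for the sponsor and DSMB to decide.

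The cost is wording and a few table columns, with no new patients or data. The downside is that some safety statements become less favourable, because the upper limit may not exclude a relevant excess.

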3.2. Study Outcome Measures

3.2.1. Primary

To measure **drug efficacy** as per standard parasitological endpoints including a) Cure Rate as defined by the proportion of children who have zero eggs per gram of stool as assessed by Kato-Katz four weeks following treatment and b) Egg reduction Rate as defined by the percent reduction in egg burden from baseline to four weeks post treatment as assessed by Kato-Katz.

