7.2. Field Based Screening

Both study sites: Screening will take place in two phases. The first phase will occur at the village level with field staff after informed consent for only the initial screening activities (urine sample for CCA testing). Children with a positive antigen test will be considered positive for schistosomiasis and eligible for potential enrolment. Parents will be given two cups (three in the Philippines) to provide stool samples collected on different days to quantify intensity of infection at baseline. Work will be performed by Ministry of Health personnel (Vector Control Division).

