7.4. Follow up at 4 weeks

Stool will be collected 4 weeks (+/- 1 week) after the baseline visit from parents at their home. Three stools will be collected to quantify egg counts by Kato Katz. Field workers will be responsible for picking up cups at this timepoint for microscopy. Technical work in this phase will be performed by Ministry of Health personnel (Vector Control Division). They will also perform the urine CCA test. **Urine** collection for:

- 2 ml tube collection for CCA/CAA testing
- **Stool** collection for:
 - Parasitology (Kato Katz assessment for schistosomiasis and geohelminths (hookworm, Ascaris, Trichuris).
- Blood- only to those children in the immunology sub-study. 7 ml of whole blood will be collected for immunology assays (such as flow cytometry, Luminex, ELISpot and ELISA).

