This sample size will give 80% power to detect differences in the secondary morbidity outcomes measures. We increase the estimated loss to follow up for these endpoints given they occur at six and 12 months following treatment. With 10% attrition, we will have 540 subjects at the 12 month follow up. As one example of the effect size we will detect for the key secondary outcome of weight-for-height z-score at 12 months, we will have 80% power to detect a difference in mean weight-for-height z-score between the six-monthly and 12-monthly dosing groups as low as 0.24 z-score, assuming a standard deviation of 1 and two-sided significance level 5% between children who received six-monthly praziquantel (either 40 mg/kg or 80 mg/kg) and children who received 12-monthly praziquantel (either 40 mg/kg or 80 mg/kg). A weight for age z-score difference of 0.23 is biologically relevant, particularly based on mitigation of only one cause of nutritional morbidity in this setting. For hemoglobin, we will be able to detect a difference of 0.29 g/dL using a standard deviation of 1.2, power of 80%, and functional sample size of 540.

For the PK study, 137 children from both sites (Uganda/Philippines) will be sampled. These are the numbers needed for 80% power to show a slope of the relationship between log CAA at 24 days and AUC is significant to $p < 0.05$. We will include 150 children to allow for loss to follow-up and enable sufficient power.

To assess immunological responses, assuming an SD of 0.9, the sub-study would require a sample size of 104 to achieve 80% power at 5% significance level for detecting difference in mean of $0.35\log_{10}$ cytokine response between the groups. We will recruit 150 children to allow for attrition.

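### No readable section schedules a pre-dose CAA: CAA clearance lacks a baseline status, and the planned log CAA on AUC slope leaves out starting worm burden and site

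*Combined protocol and SAP*

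**What the plan says.** **Pre-dose sampling.** Section 7.2 obtains "informed consent for only the initial screening activities (urine sample for CCA testing") and names no CAA. In the all-participant baseline list of section 7.3, urine appears only for the lactulose/mannitol test. Section 4.2.1 (Study visit 1) says the first void is kept as the baseline for that test, and the test precedes study drug.

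**Post-dose sampling.** CAA first appears in section 7.4, at 4 weeks: "2 ml tube collection for CCA/CAA testing". Urine is stored for CAA at 6 months (7.5) and tested at 12 months (7.6). Section 8.2.1 lists CCA/CAA without time points.

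**Analysis of clearance.** Section 11.1 compares "Schistosomal antigenic clearance assessed by CAA at 4 weeks" between doses. Section 11.4 says that "antigenic egg clearance outcomes will be analyzed using the same approach as for cure rate", and section 3.2.1 gives "Cure Rate as defined by the proportion of children who have zero eggs per gram of stool" four weeks after treatment, which is follow-up status only. The analysis set in 11.4 is intention-to-treat with complete cases: "all children will be included as randomised, regardless of whether or not they received the allocated treatment".

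**PK/PD slope.** Section 11.2 says 137 children from both sites give 80% power to "show a slope of the relationship between log CAA at 24 days and AUC is significant" at p < 0.05, and raises this to 150 for loss to follow-up. Section 11.4 uses the baseline value as a covariate only for outcomes at 6 and 12 months. For any outcome, it allows further adjustment only if key confounders differ significantly at baseline. It gives no PK/PD model.

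**The concern.** The other 4-week efficacy endpoints have a starting value. Kato-Katz infection is an entry criterion (5.1), egg reduction uses the baseline count (3.2.1), and CCA is the screening test (7.2). CAA has none in the readable text, although section 3.1.2 relies on the antigen tests to capture residual worm burden.

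Two consequences follow. First, clearance scored on week-4 status alone includes children who had nothing to clear. Second, week-4 log CAA reflects both the starting burden and the drug's effect. AUC is only partly set by randomised dose: section 3.2.2 expects it to vary with environmental enteric dysfunction, and section 2.2 describes age-dependent drug metabolism. The two sites are also two species (4.2.1). Starting burden left out of the slope is at best noise. If it is related to AUC, it confounds the exposure-response estimate, so a real relation could be missed or a spurious one reported.

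**Working it through.** **1. The plan's figure of 137.** It cannot be reproduced, because no slope, SD or correlation is given. Solving the Fisher-z formula n = ((1.960 + 0.842)/atanh r)² + 3 backwards at n = 137 gives r = tanh(2.802/√134) = 0.237, so AUC explains 0.237² = 5.6% of the variance in log CAA.

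**2. Clearance.** Inputs: two-sided 5% level; 600 × 0.93 / 2 = 279 per dose group (7% loss, section 11.2); and the plan's 70% v 82% cure rates, borrowed here as assumed CAA clearance among baseline-positive children. Let f be the assumed share CAA-negative before dosing; the documents give no figure. Observed rates are f + (1 − f) × 0.70 and f + (1 − f) × 0.82, so the difference is 12(1 − f) points. The restricted analysis keeps 12 points with 279(1 − f) per group. Power is for the uncorrected chi-squared test.

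| f | Observed rates | Difference (points) | Power, all randomised | Power, baseline-positive only |
|---|---|---|---|---|
| 0% | 70.0 v 82.0% | 12.0 | 91.5% | 91.5% |
| 5% | 71.5 v 82.9% | 11.4 | 89.6% | 90.1% |
| 10% | 73.0 v 83.8% | 10.8 | 87.5% | 88.5% |
| 20% | 76.0 v 85.6% | 9.6 | 82.3% | 84.6% |
| 30% | 79.0 v 87.4% | 8.4 | 75.7% | 79.5% |

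The fair comparison is between the last two columns: 1.0, 2.3 and 3.8 points at 10, 20 and 30%.

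**3. Slope.** In standardised form, week-4 log CAA = b × AUC + c × baseline log CAA + error. Take b = −0.237 from step 1. Let c be the assumed baseline coefficient and ρ the assumed correlation of baseline CAA with AUC. The unadjusted slope is b + cρ, and power is about Φ(|atanh slope| × √134 − 1.96).

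*No correlation (ρ = 0).* There is no bias, but adjustment sharpens the test. With c = 0.5 the partial correlation is 0.237/√(1 − 0.25) = 0.274. Then atanh(0.274) × √133 = 3.24 and Φ(3.24 − 1.96) = 90%, against 80% unadjusted. For c = 0.3, 0.5 and 0.7, the n for 80% power falls from 137 to about 126, 104 and 70.

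*With correlation, c = 0.5, unadjusted.* The last column sets b = 0 and adds both tails; it is the same for either sign of ρ.

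| ρ | Slope | Power | False-positive rate with no drug effect |
|---|---|---|---|
| +0.1 | −0.187 | 59% | 9% |
| +0.2 | −0.137 | 36% | 21% |
| +0.3 | −0.087 | 17% | 42% |

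Negative ρ exaggerates the slope instead: at ρ = −0.2 it is −0.337. The false-positive rates for |ρ| = 0.1, 0.2 and 0.3 are 6, 11 and 18% if c = 0.3, and 13, 37 and 69% if c = 0.7.

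**The case against.** - **A baseline CAA may exist.** Only the heading of Appendix A can be read, section 8.2.1 names CAA without timing, and section 11.4 defers full detail to a formal SAP. This stands: the point is that the readable visit text schedules no pre-dose CAA, not that none will be measured.
- **Few children may be CAA-negative at entry.** Section 5.1 requires Kato-Katz infection, section 14.3 confirms it, and field screening also requires a positive CCA. This stands: f could be near zero. One loose end is that section 7.2 treats an antigen-positive child as potentially eligible; it should be reconciled with 5.1 and 14.3, since antigen-only entry could raise f.
- **Randomisation protects the dose comparison.** This stands. A reader might infer that never-positive children bias one dose against the other, but they fall equally by chance. A reader might also set 76% against 92% and infer a recoverable loss of 16 points. Restriction shrinks the sample, so it recovers at most about 4.
- **Section 11.2 is a sample-size sentence, not a model.** This stands in part. A reader might infer that the PK analysis is committed to an unadjusted regression. The text does not say so, but no section supplies another model, and 11.4 plans no baseline covariate for 4-week outcomes.
- **Starting burden is already measured.** Egg counts are collected at baseline, and 11.4 names baseline intensity, site and age as effect modifiers for cure, egg reduction and morbidity. This stands, and it makes part of the fix free, but none of these is attached to the slope. Egg count is also an indirect stand-in for CAA, so it may remove only part of the problem.
- **Part of the variation in AUC is randomised.** PK children are drawn at random and dose is allocated at random, which limits ρ. It does not remove the variation within a dose group.

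**Conclusion.** The point holds as a worthwhile, low-cost improvement, subject to confirming Appendix A.

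For clearance the effect is small: mild dilution of the dose difference and inflated absolute rates, with no bias between arms. The main gain from a baseline is an endpoint that means what its name says. The power figures rest on an assumed negative share and on borrowed cure rates.

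The slope is the stronger part. As described, it omits starting burden and site, which costs about 10 points of power under the central assumption (c = 0.5, ρ = 0). It also leaves the test open to error in either direction if baseline CAA and AUC are even weakly related. The values of c and ρ are assumptions. The documents make a correlation plausible but do not show one, so they do not support saying that the slope is confounded, only that the plan does not guard against it.

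The reference to 24 days is minor: it lies within the day 21 to 35 window.

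**What to change.** 1. **Section 11.4:** specify the PK/PD model as week-4 log CAA on AUC, with site, actual days since dosing and baseline infection burden as covariates. At minimum use the baseline Kato-Katz egg count. This costs only wording.
2. **Section 7.3:** keep an aliquot of the pre-treatment urine already collected at the baseline visit after main consent, set aside before any preservative is added. Assay it for CAA, at least in the 150 PK children, and use baseline log CAA as the covariate. This is best settled before enrolment, because the model can be written later but a discarded pre-dose sample cannot be recovered.
3. **Sections 11.1 and 11.4:** where baseline CAA is available, report clearance among baseline CAA-positive children alongside the all-randomised analysis.
4. **Section 11.2:** align the 24-day wording with the 4 ± 1 week window, and state the slope or correlation behind the 137.

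The cost is one extra CAA assay per child (150 at minimum, 600 if extended to all), storage, and any consent wording needed, with no extra visit or sample. The restricted clearance analysis has a smaller denominator, which is why it sits beside the all-randomised result and does not replace it. If Appendix A already schedules a pre-dose CAA, item 2 reduces to saying so in 7.3; the other items remain.
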